#### **6.2.2. Preferred Time of Dosing**

Summary statistics to summarise percentage of total ELLIPTA doses taken at preferred time of dosing for each participant will be presented. A participant is considered as having taken their dose at their preferred time if the actual time of the ELLIPTA dose is recorded  $\pm 1$  hour of their preferred time as captured on the eCRF at screening. A histogram of individual dose deviations (in minutes) from preferred time will also be presented per treatment group. These data will also be listed.

#### **6.2.3. Study Medication Exposure and Compliance**

Duration (days) of exposure to study medication will be calculated based on randomisation date and latest (stop) of all dates recorded for the participant. Duration will be summarised categorically and with descriptive statistics. Total years exposed to Relvar/Breo after randomisation will also be presented. Further details are presented in Section 10.5 Appendix 5: Derived and Transformed Data

Calculation of Relvar/Breo study medication compliance after randomisation, will be based on the ELLIPTA device dose counter (which displays the number of doses remaining) as described in Section 10.5 Appendix 5: Derived and Transformed Data. Treatment compliance (calculated as a percentage) will be summarised categorically and with descriptive statistics.

All exposure and compliance data will be listed.

A summary of the number of puffs per day as recorded by the ELLIPTA Relvar/Breo and MDI sensors will be summarised and graphically presented.

#### **6.2.4. HCP dashboard review**

The actions taken by the HCP post the dashboard data review will be summarized and listed by visit for Arms 1 and 3.

## **7. EFFICACY ANALYSES**

### **7.1. Primary Efficacy Analysis**

The primary analysis will estimate the treatment arm effect of 6 months use of the Relvar/Breo ELLIPTA maintenance therapy with CIS when both the participant and the HCP are supplied with data from the ELLITPA sensor versus no data supplied to the participant and HCP (Arm 1 vs Arm 5).

#### **7.1.1. Endpoint**

The primary endpoint is the percentage of ELLIPTA doses taken (daily adherence) between the beginning of Month 4 and the end of Month 6 as determined by the maintenance sensor. Daily adherence is defined as the participant taking one dose of Relvar/Breo ELLIPTA, within a 24-hour period, starting at 12.00am each day of the run-in and treatment period.

#### **7.1.2. Summary Measure**

The mean difference in daily adherence between Arm 1 and Arm 5 will be estimated from an Analysis of Covariance (ANCOVA) model allowing for effects due to randomised treatment arm, baseline adherence, duration of run-in (visits), country, gender, and age (years).

#### **7.1.3. Population of Interest**

The primary efficacy analysis will be based on the Intent-To-Treat population.

### 7.1.4. Strategy for Intercurrent (Post-Randomisation) Events

The following steps in [Table 3](#) will be applied sequentially when deriving the primary endpoint. See Section [10.5.3.1](#) ELLIPTA Device Sensor Assessments for full details of the missing data imputations process.

**Table 3**

Intercurrent Event Estimation Rules (to be applied sequentially)	Intercurrent Event (IE)	Strategy with Rationale	Estimation Method following IE
1	
None (completed as randomised)
 
Without discontinuation of CIS feedback or ELLIPTA maintenance sensor
 
 
Premature discontinuation from rescue/salbutamol MDI sensor
 
Change of dose of ELLIPTA
 
 
Discontinuation of CIS feedback, but not ELLIPTA maintenance sensor
 
 
Premature discontinuation from App and/or HCP interaction
 
	
Treatment policy:
 
Directly assessed using observed adherence data while ELLIPTA maintenance sensor is in use, regardless of whether the CIS feedback is discontinued.
	Data are available; no imputation required
2	Discontinuation of ELLIPTA maintenance sensor only	
Treatment policy:
 
Without the ELLIPTA maintenance sensor, no CIS feedback is possible, assume
 
 
participants continue to take ELLIPTA as
 
	Jump to Reference (J2R) Imputation

Intercurrent Event Estimation Rules (to be applied sequentially)	Intercurrent Event (IE)	Strategy with Rationale	Estimation Method following IE
		
they would have without the CIS intervention
 
 
adherence will be like that in the control (no CIS feedback) group
 
	
3	Discontinuation of ELLIPTA	Whilst on treatment:	Follow-up after ELLIPTA discontinuation is excluded, i.e. no data; adherence is weighted by proportion of months 4 to 6 for which data is included*
4	Premature withdrawal from the study, not related to ELLIPTA discontinuation or CIS, and concurrent with discontinuation of the ELLIPTA maintenance sensor	Hypothetical:	Missing at Random (MAR) Imputation

* Discontinuation of ELLIPTA prior to the start of month 4 will lead to a participant being excluded from the primary analysis
			

#### **7.1.4.1. Events prior to premature discontinuation of the ELLIPTA maintenance sensor**

The treatment policy estimand is directly assessed using the observed adherence data while the ELLIPTA maintenance sensor is in use, regardless of whether the CIS feedback is discontinued.

Any missing intermittent adherence data will be imputed as non-adherent i.e. the participant will be assumed to have not taken their treatment within the 24-hour time period/window, where there is no evidence of device or technical/transmission failure.

Missing intermittent adherence data due to a medical device incident such as device failure, technical failure of the sensor, or data transmission failure will be assumed to be missing at random (MAR). For each participant, the percentage adherence measure will be calculated from the proportion of the number of days a participant is adherent divided by the number of days data provided in that month.

#### **7.1.4.2. Events following premature discontinuation of the ELLIPTA maintenance sensor**

It is assumed that participants would continue to take ELLIPTA as they would have without the CIS intervention (J2R imputation) following discontinuation of the ELLIPTA maintenance sensor.

It is assumed that ELLIPTA treatment is no longer appropriate if the participant discontinues ELLIPTA but remains in the study or withdraws for a reason related to ELLIPTA. The ELLIPTA adherence endpoint is no longer considered relevant and subsequent follow-up is excluded from the analysis, with participants weighted in the analysis by the proportion of months 4 to 6 for which data is included.

It is assumed that participants would continue to take ELLIPTA as they would have with their allocated CIS intervention (MAR imputation) following concurrent discontinuation of the ELLIPTA maintenance sensor and withdrawal unrelated to ELLIPTA or CIS.

See Section 10.5.3.1 ELLIPTA Device Sensor Assessments for further derivation details.

#### **7.1.5. Statistical Analyses / Methods**

Details of the planned displays will be provided in Section 10.8, Appendix 8: List of Data Displays and will be based on GSK data standards and statistical principles.

Unless otherwise specified, endpoints /variables defined in Section 7.1.1, Endpoint will be summarised using descriptive statistics, graphically presented (where appropriate) and listed.

### 7.1.5.1. Statistical Methodology Specification

Endpoint / Variables
The primary endpoint is the percentage of ELLIPTA doses taken (daily adherence) between the beginning of Month 4 and the end of Month 6 as determined by the maintenance sensor. Daily adherence is defined as the participant taking one dose of Relvar/Breo ELLIPTA within a 24 hour period, starting at 12.00am each day of treatment period.
Multiple Imputation Specification
Imputation will be carried out using monthly adherence rates for months 1 to 6. 1000 draws will be used. For each draw, four intermediate imputation datasets will be created to allow for the handling of fully unobserved months (using set A imputations) and partially unobserved months (using set B imputations).

 
• Set A where the partially observed month is directly estimated under the MAR assumption as the proportion of the number of days a participant is adherent divided by the number of days data provided in that month. 
 
• J2R imputations
 
• MAR imputations
 
 
 
• Set B where the partially observed month is set to missing. 
 
• J2R imputations
 
• MAR imputations
 
 
 

The timing of the intercurrent events of discontinuation of the ELLIPTA maintenance sensor, discontinuation of ELLIPTA and withdrawal from study will be used to identify the proportion of each month to be assigned as observed data, J2R imputed data, MAR imputed data, or no data. The strategy for handling intercurrent events is described in Section 7.1.4 Strategy for Intercurrent (Post-Randomisation) Events.
 
Within each imputation draw, for each month, the observed and any imputed data will be combined to provide a percentage adherence value. The values for months 4 to 6 will be combined to create the value for the primary analysis and the weight to be assigned to each participant.
 
Multiple imputation using Rubin's rules will be used to estimate the treatment effect and associated standard error, by performing the ANCOVA analysis described below on the primary endpoint within each dataset.
 
The multiple imputation will be implemented using the methods described in Carpenter, 2013, using the macros available from https://missingdata.lshtm.ac.uk/2017/04/06/gsk-five-macros/.

Model Specification

The analysis will be performed on the percentage adherence between Months 4 and 6 using an Analysis of Covariance (ANCOVA) model allowing for effects due to randomised treatment arm, baseline adherence, duration of run-in (visits), country, gender, and age (years).
 
Baseline adherence will be the percentage ELLIPTA doses taken (daily adherence) during the last 28 days of the run-in period prior to randomisation. Randomised treatment arm, duration of run-in (visits), country, and gender will be included as categorical covariates; baseline adherence and age (years) will be included as continuous covariates.

Each participant will be weighted by the proportion of months 4 to 6 for which data is included in the percentage adherence endpoint (both observed and imputed data are accounted for in the weighting).

Data from all 5 treatment arms will be included in the model and used to estimate the difference between Arm 1 and Arm 5 for the primary objective.

#### **Model Checking & Diagnostics**

Normality assumptions underlying the ANCOVA model used for analysis will be examined in a limited number of imputed datasets by obtaining a normal probability plot of the residuals and a plot of the residuals versus the fitted values (i.e. checking the normality assumption and constant variance assumption of the model respectively) to gain confidence that the model assumptions are reasonable.

If there are any departures from the distributional assumptions, alternative models may be explored using appropriately transformed data.

Interactions with treatment will be explored for other model covariates and tests for interactions will be at the 2-sided 10% significance level. Any significant interactions that are found will be thoroughly investigated and where necessary, extra outputs will be produced.

#### **Model Results Presentation**

Summary statistics (n, mean, standard deviation, median, minimum, maximum) of the primary endpoint will be provided, based on the observed percentages.

The adjusted means for each treatment and the estimated treatment difference for the primary treatment comparison of Arm 1 versus Arm 5 will be presented together with a 95% confidence interval for the difference and corresponding Wald test statistic and p-value from the multiple imputation procedure.

#### **Subgroup Analyses**

For the analysis by baseline total ACT score (<=15, 16-19), the model will additionally include the baseline ACT total score category and randomised treatment arm-by-baseline ACT total score category interaction as covariates.

For the analysis by age group (18-35, 36-48, 49-58, >58 years), the model will additionally include age group and randomised treatment arm-by-age group interaction as covariates.

The adjusted means for each treatment and the estimated treatment difference for the treatment comparisons of Arm 2 versus Arm 5, Arm 3 versus Arm 5 and Arm 4 versus Arm 5 will be presented together with the 95% confidence interval for the differences and corresponding p-values from the multiple imputation procedure.

#### **Sensitivity Analysis**

- A sensitivity analysis will be performed estimating the treatment effect by utilizing a generalized linear model (GLM) and not running the multiple imputation process. The model will follow a binomial distribution with the logit link function. The covariates included in the GLM will be the same as those included in the primary analysis. Model assumptions will be checked using standardised residual plots, and model results presentation will be the same as described for the primary analysis. Missing data will be assumed to be MAR.

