
STEP 4: Creating the Monthly Analysis values dataset
 
For each month within each participant create a count of each of the following durations based on intercurrent events: Let,
 
<math>m1</math> = maintenance sensor still in use
 
<math>m2</math> = maintenance sensor discontinued, but ELLIPTA Relvar/Breo not discontinued
 
<math>m3</math> = ELLIPTA Relvar/Breo discontinued (includes days post withdrawal from the study). Note, if participant is a completer then for Analysis Month 6, <math>m3=0</math>.
 
<math>m4 = m1 + m2 + m3</math>
 
Calculate the proportion of days the sensor was still in use from the total number of days ELLIPTA was in use within a month, <math>m1/(m1+m2)</math>
 
Calculate the proportion of days the sensor was discontinued from the total number of days ELLIPTA was in use within a month, <math>m2/(m1+m2)</math>
 
Set participants monthly values to observed, MARA, MARB, J2RA, J2RB imputation, no data each with an <math>m1</math>, <math>m2</math>, <math>m3</math> and <math>m4</math> duration.

Percentage of ELLIPTA doses taken (daily adherence) Endpoint												
--	--	--	--	--	--	--	--	--	--	--	--	--

Examples include to following:

- A participant who prematurely discontinues sensor after 15 days of Analysis Month 5 and concurrently discontinues ELLIPTA maintenance therapy and study withdrawal after 10 days of Analysis Month 6

Subject Id	Draw	Month	A	B	J2RA	J2RB	MARA	MARB	m1	m2	m3	m4
X	1	1	77	77	77	77	77	77	28	0	0	28
X	1	2	82	82	82	82	82	82	28	0	0	28
X	1	3	87	87	87	87	87	87	28	0	0	28
X	1	4	77	77	77	77	77	77	28	0	0	28
X	1	5	71	.	71	77	71	78	15	13	0	28
X	1	6	.	.	80	79	77	76	0	10	18	28

- A participant who concurrently prematurely discontinues sensor, ELLIPTA maintenance therapy and study withdrawal after 15 days of Analysis Month 5

Subject Id	Draw	Month	A	B	J2RA	J2RB	MARA	MARB	m1	m2	m3	m4
X	1	1	77	77	77	77	77	77	28	0	0	28
X	1	2	80	80	80	80	80	80	28	0	0	28
X	1	3	79	79	79	79	79	79	28	0	0	28
X	1	4	75	75	75	75	75	75	28	0	0	28
X	1	5	83	.	83	77	83	79	15	0	13	28
X	1	6	.	.	77	77	75	80	0	0	28	28

- A participant who completes the study after 26 days in Analysis Month 6

Subject Id	Draw	Month	A	B	J2RA	J2RB	MARA	MARB	m1	m2	m3	m4
X	1	1	77	77	77	77	77	77	28	0	0	28
X	1	2	82	82	82	82	82	82	28	0	0	28
X	1	3	87	87	87	87	87	87	28	0	0	28
X	1	4	77	77	77	77	77	77	28	0	0	28
X	1	5	80	80	80	80	80	80	28	0	0	28
X	1	6	82	82	82	82	82	82	15	11	0	26

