
STEP 5: Primary and Secondary Percentage of ELLIPTA doses taken Endpoints calculation
 
The calculations presented in the previous steps support the final derivation of the following primary and secondary endpoints, the percentage of ELLIPTA doses taken between
 
 
the beginning of Month 4 and the end of Month 6
 
the beginning of Month 1 and the end of Month 6
 
the beginning of Month 1 and the end of Month 3
 
 
For participants who complete the study treatment (i.e. no premature discontinuation of ELLIPTA Relvar/Breo) during the endpoint period of interest:
 
Analysis Endpoint is the average of monthly Analysis Values over the number of months in the endpoint period of interest, i.e.
 
 
Month 4 to Month 6
 
Month 1 to Month 6
 
Month 1 to Month 3
 
 
For participants who prematurely discontinue ELLIPTA during the endpoint period of interest for reasons related to ELLIPTA, then the weight is the total duration on ELLIPTA within the endpoint period of interest and applied to each analysis month based on the duration within that month. This weight should be applied to each monthly Analysis value within the period of interest and results summed together to produce the final endpoint/response variable for modelling within macro Part 3.

Percentage of ELLIPTA doses taken (daily adherence) Endpoint
---

Note the weight is, total duration of ELLIPTA use within the period of interest . The proportion of weight to apply per monthly Analysis value is  $m1+m2/\text{total duration of ELLIPTA use within the period of interest}$

For participants who prematurely discontinue ELLIPTA during the endpoint period of interest for reasons not related to ELLIPTA or CIS, or just related to CIS, the MAR or J2R imputation assumes participants would have continued taking ELLIPTA until the end of the period of interest. The weight is the total duration within the endpoint period of interest. This weight will be applied to each monthly Analysis value within the period of interest and results summed together to produce the final endpoint/response variable for modelling within macro Part 3.

Note the weight is, total expected ELLIPTA duration within the period of interest. The proportion of weight to apply per monthly Analysis value is  $m1+m2+m3/\text{Total expected ELLIPTA duration within the period of interest}$ .

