Percentage of ELLIPTA doses taken (daily adherence) – Sensitivity Analysis
---

Sensitivity analyses will be performed estimating the treatment effect by utilizing a generalized linear model (GLM) and not running the multiple imputation process. The model will follow a binomial distribution with the logit link function.

The sensitivity analyses will be performed for the following primary and secondary endpoints relating to the percentage of ELLIPTA doses taken between

- the beginning of Month 4 and the end of Month 6
- the beginning of Month 1 and the end of Month 6
- the beginning of Month 1 and the end of Month 3

Model assumptions will be checked by using standardised residual plots. Missing data will be assumed to be MAR.

The weighting strategy is to be applied as detailed above.

Percentage of ELLIPTA doses taken (daily adherence) Endpoint
---

Seeds for Multiple Imputations Macros
--

Seeds for all planned MI analyses were determined in advance using the following SAS code and documented within this RAP prior to unblinding:

```
data temp;
do i = 1 to 6;
  number=round(10000*ranuni(0),1);
  output;
end;
run;
proc print;
run;
```

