## EFFICACY TABLES

Example : EFF\_T1

Protocol : 207040

Population : Intent-to-Treat

Page 1 of x

Table 2.01

Summary of Monthly Percentage of ELLIPTA doses taken (daily adherence) between the beginning of month 1 and end of month 6 as determined by the maintenance sensor – Observed Monthly Data

Month		Arm 1 (N=xxx)	Arm 2 (N=xxx)	Arm 3 (N=xxx)	Arm 4 (N=xxx)	Arm 5 (N=xxx)
Baseline (%)	n	XX	XX	XX	XX	XX
	Mean	XX.X	XX.X	XX.X	XX.X	XX.X
	SD	X.XX	X.XX	X.XX	X.XX	X.XX
	Median	XX.X	XX.X	XX.X	XX.X	XX.X
	Min.	XX	XX	XX	XX	XX
	Max.	XX	XX	XX	XX	XX
Month 1 (%)	n	XX	XX	XX	XX	XX
	Mean	XX.X	XX.X	XX.X	XX.X	XX.X
	SD	X.XX	X.XX	X.XX	X.XX	X.XX
	Median	XX.X	XX.X	XX.X	XX.X	XX.X
	Min.	XX	XX	XX	XX	XX
	Max.	XX	XX	XX	XX	XX
Average Month 1 to 6 (%)	n	XX	XX	XX	XX	XX
	Mean	XX.X	XX.X	XX.X	XX.X	XX.X
	SD	X.XX	X.XX	X.XX	X.XX	X.XX
	Median	XX.X	XX.X	XX.X	XX.X	XX.X
	Min.	XX	XX	XX	XX	XX
	Max.	XX	XX	XX	XX	XX

Programming note: Continue table to include all monthly timelines (month2, month 3, month 4, month 5, month 6, average month 4-6, average month 1-3, average month 1-6)

Example : EFF\_T2  
 Protocol : 207040  
 Population : Intent-to-Treat

Page 1 of 1

Table 2.02

Summary of Statistical Analysis of Percentage of ELLIPTA doses taken (daily adherence) between the beginning of month 4 and the end of month 6 as determined by the maintenance sensor

Month 4 to 6 (%)	Arm 1 (N=xxx)	Arm 2 (N=xxx)	Arm 3 (N=xxx)	Arm 4 (N=xxx)	Arm 5 (N=xxx)
n	xx	xx	xx	xx	xx
LS Mean (Std Error)	xx.x	xx.x	xx.x	xx.x	xx.x
CIS Arm vs Arm 5					
Difference	xx.x	xx.x	xx.x	xx.x	xx.x
95% C.I.	(x.xx, x.xx)				
p-value	xx.XXX	xx.XXX	xx.XXX	xx.XXX	xx.XXX

[1] Monthly adherence values were weighted by amount of observed data available and time on ELLIPTA between month 4 and 6

Example : EFF\_T3

Protocol : 207040

Population : Intent-to-Treat

Page 1 of 1

Table 2.xx

Summary of Statistical Analysis of Percentage of ELLIPTA doses taken (daily adherence) between the beginning of month 4 and the end of month 6 as determined by the maintenance sensor by Baseline ACT Total Score Group

Table 2.xx

Summary of Statistical Analysis of Percentage of ELLIPTA doses taken (daily adherence) between the beginning of month 4 and the end of month 6 as determined by the maintenance sensor by Age Group

Example : EFF\_T4

Protocol : 207040

Population : Intent-to-Treat

Page 1 of 1

Table 2.xx

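### The SAP's only sensitivity analysis of the primary endpoint is a binomial-logit model with no stated trials and no allowance for extra-binomial variation, so its confidence interval and p-value cannot be relied on

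*SAP*

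**What the plan says.** SAP 7.1.5.1, under Sensitivity Analysis, replaces the multiple-imputation ANCOVA by a generalised linear model (GLM) with the same covariates, taking missing data as missing at random. On the distribution it says only "The model will follow a binomial distribution with the logit link function". Residual plots are the sole check, with no action attached. Results are to be presented as for the primary analysis. That means adjusted means, the Arm 1 versus Arm 5 difference, a 95% interval and a p-value that the primary text takes from the imputation procedure, which this model does not run.

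SAP 7.2.1.5.1 to 7.2.1.5.3 repeat the model for the secondary adherence analyses (months 4-6, 1-6 and 1-3). SAP 10.5.3.1 repeats it again and adds "The weighting strategy is to be applied as detailed above".

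The weighting is described in several places:

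- SAP 7.1.5.1, Model Specification: "Each participant will be weighted by the proportion of months 4 to 6 for which data is included", with the remark that "both observed and imputed data are accounted for in the weighting".
- SAP 10.5.3.1, STEP 5, for those stopping ELLIPTA for unrelated reasons: "Note the weight is, total expected ELLIPTA duration within the period of interest".
- The same step, for treatment completers: "Analysis Endpoint is the average of monthly Analysis Values over the number of months in the endpoint period of interest".
- The footnote of shell EFF_T2, which Appendix 8 assigns to the GLM table (2.3): "Monthly adherence values were weighted by amount of observed data available and time on ELLIPTA".

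Protocol 11.4.1 promised sensitivity analyses by multiple imputation under differing assumptions for withdrawn subjects. The SAP specifies none, and its table of changes from the protocol (Table 1) does not list their removal.

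**The concern.** ANCOVA estimates its residual variance from the data, so a constant factor in the weights cancels. A binomial model with scale 1 does not estimate a variance: the mean and the number of trials fix the standard error. Whether a completer counts as 84 or as 1 then decides the width of the interval, and the SAP does not say which applies.

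Neither choice matches how adherence behaves. Days within a person are strongly correlated, so 84 independent trials imply far too little spread between people. A single trial per person implies too much. This is the only robustness check specified for the primary result. One reading would make it almost always appear to confirm an effect, and the other would make it fail too often when the effect is real.

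**Working it through.** **Inputs.** SD 28 points, 76 evaluable per arm, 15-point target, two-sided 5% (protocol 11.2.1). Months 4 to 6 run from Day 85 to Day 168, so 168 - 85 + 1 = 84 days (SAP Table 5). The published study's arms have mean (SD) 88% (16%) and 66% (27%) (protocol 11.2.2). Assumptions: means m from 66% (that study's control arm) to 81% (plus 15 points), and multiple correlation R of the covariates from 0 to 0.7.

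**The plan's own figure.** Power for 76 per arm, 15 points and SD 28 is 0.910 (0.907 with the noncentral t), against about 90% stated. All seven rows of protocol Table 2 reproduce within 2 points. The documents give no figure for the GLM.

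**Spread implied by the binomial.** With 84 independent days, sqrt(0.66 × 0.34/84) = 5.2 points and sqrt(0.81 × 0.19/84) = 4.3 points. With one trial per person, sqrt(0.66 × 0.34) = 47 points and sqrt(0.81 × 0.19) = 39 points. The planning value is 28.

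**Error in the standard error.** True residual variance V = SD²(1 - R²). Average binomial variance given the covariates B = m(1 - m) - R²SD². With days as trials or weights, the model SE is too small by sqrt(84V/B). With a fraction of weight 1, it is too large by sqrt(B/V).

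| m | R | Days: too small by | Fraction: too large by |
|---|---|---|---|
| 0.66 | 0 | 5.42 | 1.69 |
| 0.66 | 0.5 | 4.91 | 1.87 |
| 0.66 | 0.7 | 4.25 | 2.16 |
| 0.81 | 0 | 6.54 | 1.40 |
| 0.81 | 0.5 | 6.06 | 1.51 |
| 0.81 | 0.7 | 5.39 | 1.70 |

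For example, at m = 0.66 and R = 0.7, V = 0.0784 × 0.51 = 0.0400 and B = 0.2244 - 0.0384 = 0.1860. So sqrt(84 × 0.0400/0.1860) = 4.25.

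**Using the published arms alone, with no assumed mean or R.** The ratio is sqrt(0.16² + 0.27²)/sqrt((0.88 × 0.12 + 0.66 × 0.34)/84) = 5.0 too small, or 1.8 too large for the fraction.

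**Other ranges.** Over the Table 2 SDs of 22 to 34 with the same m and R, the ranges are 3.2 to 7.9 (days) and 1.15 to 2.85 (fraction). For months 1-6, if SD 28 holds over 168 days, the days reading gives 6.0 to 9.0 with R from 0.3 to 0.7.

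**Effect on the test.** When the SE is too small by a factor k, null rejection is 2(1 - Φ(1.96/k)). This gives 0.65 at k = 4.25 and 0.76 at k = 6.54. Beta-binomial simulation with 76 per arm and one baseline covariate (R 0.3 to 0.7) gave 0.648 to 0.758 for days and at most 0.0042 for the fraction. Without covariates, power for 66% versus 81% on the fraction reading was about 0.58 to 0.60, against 0.90 with an estimated scale.

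**Where the plain binomial would be right.** This needs B/V trials per person, which runs from 1.96 (m = 0.81, R = 0) to 4.65 (m = 0.66, R = 0.7). Three unit-weight monthly fractions would give a true-to-model SE ratio of 0.80 to 1.24.

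**Remedy checked.** Simulated null rejection was 4.2% to 6.4% with Pearson scaling across the two sets of runs, and 4.8% to 5.7% with a sandwich variance. In the unadjusted runs Pearson scaling gave the same power, 0.90, for weights of 1 and 84.

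**Weight example.** STEP 4 describes "A participant who concurrently prematurely discontinues sensor, ELLIPTA maintenance therapy and study withdrawal after 15 days of Analysis Month 5". Observed days in months 4 to 6 are 28 + 15 + 0 = 43. If the withdrawal is unrelated to ELLIPTA, the STEP 5 weight is 84. Counting observed data only, the proportion is 43/84 = 0.51.

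**The case against.** **A reader might infer that the standard errors are wrong however response and weight are read.** The documents do not support that. Three monthly fractions would come out about right, and the EFF_T2 footnote does speak of monthly values. But the match is a coincidence of these SDs, the SAP never defines such a response, and STEP 5 forms one summed value per participant.

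**A reader might infer that the SAP fixes the dispersion at 1.** It is silent. A programmer could add a scale option, and estimated dispersions of 18 to 41 in the covariate simulations would be hard to miss in residual plots. The rejection rates are therefore conditional on a plain binomial variance. That is still the variance the stated distribution implies. No action follows the plots, and the clause allowing alternative models in 7.1.5.1 is written for the ANCOVA.

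**A reader might infer that the weight definitions are irreconcilable.** That is too strong. Without imputation, included data in 7.1.5.1 can be read as observed data only. The same section gives completers a weight of 1. The footnote also mentions time on ELLIPTA, which overlaps with STEP 5. The factor between days and proportion cancels once the scale is estimated. What stands is that the SAP does not say which form the GLM uses, and that imputed time has no place in it.

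**Importance.** The primary inference is untouched and no success rule uses this model. Both points stand and limit the concern to how the robustness check can be read.

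**Conclusion.** The concern holds in this form: the model's variance is left to an unstated choice, and both weight scales the SAP describes give a wrong plain-binomial SE. It is about 4.3 to 6.5 times too small on the days reading and about 1.4 to 2.2 times too large on the fraction reading. These sizes rest on the protocol's SD of 28, which it calls conservative, and on the assumed means and R. The published arms alone give 5.0 and 1.8.

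The point estimates under a given weighting do not depend on the variance choice. The interval and p-value do, and they could not be used to judge whether the primary result is robust. The point should be fixed, although it does not threaten the primary conclusion.

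The missing multiple-imputation sensitivity analyses are a separate discrepancy between protocol and SAP. They do not bear on the SE argument.

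**What to change.** 1. Prespecify a Pearson-scaled (quasi-binomial) or participant-level sandwich variance. Either restores about 5% type I error and removes the dependence on the scale of the weight.
2. State the response and one weight that counts observed data only. There are two workable choices. The first is the average of monthly observed fractions, weighted by the observed proportion of the period. It keeps the within-month missing-at-random rule of SAP Table 1 and the monthly averaging of STEP 5. The second is adherent days out of days with data (D1 out of D5 - D2 - D3 in STEP 1), with no further weight. It pools months by available days and so departs from those two rules.
3. State how logit estimates become the percentage-point difference that the presentation paragraph requires, for example by standardising the fitted probabilities.
4. Apply the same text to months 1-6 and 1-3.
5. Separately, restore the multiple-imputation sensitivity analyses of protocol 11.4.1, reusing the planned macros, or list and justify their removal in SAP Table 1.

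Items 1 to 4 cost one variance option and a few sentences, plus the pooling across months if the second response is chosen. No data collection or design change is needed.
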